#### 9.4 Randomization/Stratification Factors

Blocked randomization with equal allocation will be utilized with adjustment in randomization sequence to account for the potential to drop an arm. Block size is 2 times the number of treatment arms. Randomization will be stratified by outpatient or inpatient status at time of enrollment into the trial.

Randomization lists will be generated prior to study enrollment and provided to the IDS pharmacist who will be in charge of the randomization with the randomization coordinator. All other study personnel including the PIs will be blinded to the randomization lists to prevent patient and investigator bias. Patients who are eligible for randomization will be assigned to a treatment arm according to the randomization list.

In the scenario where a treatment arm is terminated early or a new treatment is added into the study, a new randomization list may be generated to replace the existing one. The randomization list will give every patient equal probability to each study arm that is currently available.

The randomization list will be incorporated into the OnCore Clinical Trials Management System and accessible to the IDS pharmacist. This is facilitated by the OnCore CTMS which assigns different access and restriction levels depending on personnel role in the study. Treatment allocation for each patient is thus performed by the IDS pharmacist after Study Coordinator confirms patient eligibility status.

## **9.5 Statistical Analysis Plan**

The primary analysis will include estimate of the rate of stability in clinical scale (less than 2 point decrease in COVID 7-POINT ORDINAL SCALE) for each arm along with exact binomial 90% confidence interval. This is based on the first response in clinical scale after enrollment and randomization into the trial. In addition, the Bayesian posterior probability of the response rate being greater than 90% will be calculated for each arm at the end of the trial. The rates of development of severe respiratory or organ failure, clearance of viral RNA at day 28 and mortality will be summarized in each arm. Changes in SARS-CoV-2 RNA as detected by polymerase chain reaction (PCR) over time will be summarized in each treatment arm and compared using paired tests or longitudinal linear models.

Secondary endpoints related to proportion of outcomes as indicated in Section 9.2 will be estimated along with exact confidence intervals while descriptive statistics including median, range, IQR will be calculated for the duration in days of efficacy outcomes. Survival analysis methods will be utilized to estimate time to event endpoints. The exploratory and correlative endpoints such as inflammatory markers and cytokine levels will be summarized at baseline and follow-up time points. Changes from baseline will be compared using paired test or longitudinal linear mixed models.

Secondary analyses will include estimates of rate and confidence intervals of stability in clinical scale (less than 2 point decrease in COVID 7-POINT ORDINAL SCALE) either from the outpatient or inpatient continuum using subgroup analyses or logistic regression with a variable to account for response status among outpatients for each arm.

All patients who received study drugs will be included in the safety analysis. The maximum grade of toxicity for each category of interest will be recorded for each patient and summary results will be tabulated by category and grade. We will describe all serious ( $\geq$  grade 3) toxicity events. Frequency and incidence tables of toxicity and AEs will be generated in each treatment arm. Likewise, proportions of specific safety endpoints in Section 9.2 will be summarized.

m-ITT population is defined as all patients who have been randomized and received at least one dose of the study treatment. The primary analysis will be based on the m-ITT population.

Handling of missing data: The primary endpoint is based on a simple 7-scale assessment and is unlikely to be missing. Patients who are in the m-ITT population but have missing primary endpoints will be classified as non-responders to the treatment.

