## **2.6 Rationale**

We propose the use of a multi-arm, phase II “pick-the-winner” trial design to allow initial assessment of multiple therapies in parallel and selection of promising therapies with adequate probabilities after COVID19 + testing in high risk, but non-critically ill individuals. [47] Prior to moving a promising therapeutic agent forward into large randomized trials of this therapy versus placebo, investigators need to provide substantial evidence of effectiveness and adequate characterization of safety. In addition, we incorporate rapid futility analysis where each agent is assessed independently using Bayesian posterior probability calculations. **NOTE: this is based on efficacy not toxicity assessment. The toxicity assessment will be done using run-ins for some of the arms.** This selection design approach along with interim assessments of efficacy,, used often in other disciplines such as oncology, allows for initial assessment of potential benefit using statistical probability calculations, before designing randomized comparative trials to avoid exposing large numbers of subjects to potentially futile agents. The “pick the winner” trial design and Bayesian posterior probability methods allow for an adaptive, proof-of-concept strategy which incorporates prospectively planned criteria to stop each arm independently for futility,[48] [49] with the prospect of expanding from a proof-of-concept phase to a larger confirmatory trial, typically a randomized, placebo controlled trial, if initial assessments are positive. The hypothesis of this study is that the addition of agents that inhibit viral entry or replication of SARS-CoV-2 virus, will be devoid of additional moderate to severe toxicities, will prevent clinical deterioration at 14 days, and will improve viral clearance at Day 14 in high risk individuals. Additionally, we hypothesize that clinical outcomes in COVID-19 infected patients at higher risk of poor outcomes following infection will be improved compared to the emerging standards when introduced as an early intervention after diagnosis.

COVID 7-point Ordinal Outcome Scale and Primary Endpoint

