#### 6.1 Agent Administration

The CURE Alliance Drug Steering Committee will serve as the drug selection committee to identify the appropriate new drugs for each new arm of this clinical trial. Treatment will be administered on an outpatient or inpatient basis provided that entry criteria are met. If emerging data indicates futility of a medication in one or more arms of our study, and was tested in a similar patient population in a randomized clinical trial or trials, the study drug selection committee may recommend removal of that drug treatment arm for futility with approval of the study team. Once a futility endpoint is met in an arm, we will replace that arm with the next appropriate proposed arm with approval of the CURE Alliance Drug Steering Committee. **All subjects receive standard supportive treatment throughout their infection, whether outpatient or during inpatient hospitalization.** Reported adverse events and potential risks are described in Section 10.

Treatment regimens will be evaluated and novel agents selected by the steering committee. Should drug supply become unavailable that arm would pause until drug supply is available.

Regimen Description- Arm C				
Agent	Formulation Strength	Daily Dose	Route	Schedule
Ivermectin	3 mg tablet	12-15 mg	Oral	Weight < 75kg: 4 tabs on Days 1 and 2, (12 mg total daily dose) Weight ≥ 75kg: 5 tabs on Days 1 and 2, (15 mg total daily dose)

Regimen Description- Arm D				
Agent	Formulation Strength	Daily Dose	Route	Schedule
Camostat Mesilate	100 mg tablet	600mg	Oral	2 tab TID after a meal (600 mg total daily dose) Days 1-14

Regimen Description- Arm E				
Agent	Formulation Strength	Daily Dose	Route	Schedule
Artemisia annua tea or coffee	Decaf coffee 450mg per pod Tea 225mg per bag	1350 mg	Oral	One 8oz brewed tea (two bags) or one coffee pod TID Days 1-14

Regimen Description- Arm F				
Agent	Formulation Strength	Daily Dose	Route	Schedule
Artesunate	100mg	200mg	Oral	Two tabs once day (200mg total) Days 1-14

Patients will be assigned to a treatment arm according to the randomization process described in Section 9 of this protocol

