## 9. STATISTICAL CONSIDERATIONS

### 9.1 Study Design/Endpoints

This study is a randomized, multi-arm phase II trial. No proven effective therapies currently exist for COVID19 (Sanders J et al. JAMA April 13, 2020), thus a selection design using the frequentist pick-the-winner design will be employed as early screening for promising therapies. The primary objective is to rapidly evaluate multiple potential inhibitors of SARS-CoV-2 viral replication in COVID19 positive patients with high-risk factors in order to decrease clinical deterioration, defined as a less than 2 point decrease in initial COVID 7-POINT ORDINAL OUTCOMES SCALE within 14 days from study entry (primary). As an example, if a person enters the study at ORDINAL SCALE 6 and does not worsen to 4 or less, that is considered a success.

For each arm a phase I lead in portion, six patients per group will be followed in order to evaluate dose limiting toxicities and preliminary safety. If 2 of the first 5 patients or if  $\geq 2$  of 6 patients experience DLT, the regimen will not be considered safe for further evaluation.

The trial will be powered based on the primary endpoint of the rate of patients who will exhibit less than 2 levels of decrease in COVID 7-POINT ORDINAL SCALE from baseline to Day 14. The goal of selection designs is to select with high probability should a superior treatment exist. Note that hypothesis testing or comparisons between arms or with a placebo is not performed with this design and subsequent trials are needed for definitive hypothesis testing of the promising arm.

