### **9.3 Sample Size/Accrual Rate**

The assumption is that transition rate for deterioration in clinical scale is equal to 20% for the high-risk patients to be enrolled in this trial based on a recent MMWR report from the CDC. The goal is to determine if any of the candidate treatments will exhibit a 50% reduction in deterioration of clinical status (i.e. deterioration rate = 10%). Thus, baseline stability in clinical scale (decrease less than 2 points in COVID 7-POINT ORDINAL SCALE) is assumed to be 80% and an improvement to 90% of all patients remaining stable (decrease less than 2 points in COVID 7-POINT ORDINAL SCALE) is hypothesized. A sample of 60 patients in each arm is proposed. If there is a clear superior treatment as shown in scenarios A and B below, there is at least an 82% selection probability. If the clinical response rate across arms are not very different, the probability of selecting the superior treatment is at 70% and is much higher compared to the other treatments (scenario C); while there is an equal chance of selecting arms that have similar superior efficacy (scenario D).

Scenario A	Response Rate	n	Selection Probability
Trt 1	.80	60	.035
Trt 2	.80	60	.035
Trt 3	.80	60	.035
Trt 4	.90	60	.822

Scenario C	Response Rate	n	Selection Probability
Trt 1	.80	60	.026
Trt 2	.80	60	.026
Trt 3	.85	60	.146
Trt 4	.90	60	.700

Scenario B	Response Rate	n	Selection Probability
Trt 1	.80	60	.002
Trt 2	.80	60	.002
Trt 3	.85	60	.019
Trt 4	.95	60	.949

Scenario D	Response Rate	n	Selection Probability
Trt 1	.80	60	.011
Trt 2	.80	60	.011
Trt 3	.90	60	.421
Trt 4	.90	60	.421

Interim monitoring to assess futility or efficacy will be performed during the trial using the Bayesian posterior probability (See Section 9.6). If a total of 60 patients is enrolled in an arm, the proposed sample size will provide an estimate of clinical success rate with width of a two-sided 90% confidence interval (CI) equal to 0.143 assuming a response rate = 0.90; specifically, a 90% two-sided exact binomial CI = 0.81 – 0.95.

Based on this current design, we plan to enroll a maximum of 240 total patients.

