## **9.6 Interim Analysis**

The timing of interim analysis will be based on rate of patient accrual. An initial interim analysis will be performed after 10 patients are randomized in each arm. Futility and efficacy will be assessed in each treatment arm by calculating Bayesian posterior probabilities. The beta distribution for the efficacy/success rate is utilized with a non-informative Jeffrey's prior equal to beta (0.5, 0.5). Specifically, a futility rate  $\leq$  80% will be assumed and the probability for stopping for futility will be set at 70%. An efficacy rate  $\geq$  90% will be assumed and a

probability for early stopping for efficacy set at 90%. Based on these assumptions, the futility stopping boundary for the first 10 patients in each arm is set at  $\leq 7$  patients with clinical stability (i.e. less than 2 point decrease in COVID 7-POINT ORDINAL SCALE) in a specific treatment arm.

The Bayesian methodology allows flexibility in the timing and cohort size in each arm in the conduct of each interim analysis. Thus, depending on patient enrollment and cohort size in each arm, subsequent interim analyses will be performed (e.g. after every 10 additional patients in each arm) and additional stopping bounds will be calculated. ***Real-time assessments of patient response will be critical and will be facilitated by close coordination of clinical and research teams.***

**The decision making process for this trial such as dropping an arm or other changes on how to proceed with the trial will be based on clinical and safety considerations along with newly developing information on COVID19 as well as guidance by results of efficacy estimates and interim posterior probabilities.**

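### Does the final analysis need a stated comparison of the leading arm with the 80% no-benefit rate?

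*Combined protocol and SAP*

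**What the plan says.** All references are to the combined protocol and SAP.

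- **Section 9.3** gives the planning rates: stability "is assumed to be 80% and an improvement to 90% of all patients remaining stable". The stated goal is a halving of deterioration from 20% to 10%, which is the 90% stability target. Each of the four arms has 60 patients, and the sample size rests on the probability that the best arm ranks first.
- **Section 9.5** reports the stability rate "for each arm along with exact binomial 90% confidence interval". It adds that "the Bayesian posterior probability of the response rate being greater than 90% will be calculated for each arm at the end of the trial". No threshold is attached to that posterior.
- **Section 9.6** uses 80% as the per-arm futility reference (stop if the posterior probability of a rate at or below 80% reaches 70%) and 90% as the efficacy reference. Decisions are taken with "guidance by results of efficacy estimates and interim posterior probabilities", among other considerations.
- **Section 2.6** describes "prospectively planned criteria to stop each arm independently for futility", and **Section 6.1** says: "Once a futility endpoint is met in an arm, we will replace that arm with the next appropriate proposed arm".
- **Section 9.1** states that "hypothesis testing or comparisons between arms or with a placebo is not performed with this design and subsequent trials are needed" for a definitive answer.

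**The concern.** The only posterior planned for the end of the trial is measured against 90%, the hoped-for rate, and not against 80%, the rate expected without benefit. An arm that performs exactly as hoped gets a posterior near one half, which says nothing direct about whether it beats no benefit. A ranking design also usually produces a leader, even when every arm is at 80%, and the Section 9.3 table has no such scenario. No passage says that the leader's result is to be read against 80% before it is called promising. The best of four useless arms might then be carried into a confirmatory trial.

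**Working it through.** **Inputs.** From Section 9.3: p0 = 0.80, p1 = 0.90, n = 60 per arm, four arms. From Section 9.6: prior beta(0.5, 0.5), first look at 10 patients per arm, later looks for example every 10. Section 9.5 names no prior, so that of Section 9.6 is assumed to carry over.

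**Step 1: the plan's own figures.** An arm is selected if its count is strictly highest:

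P(select i) = Σₓ P(Xᵢ = x) · Πⱼ≠ᵢ P(Xⱼ ≤ x − 1), X binomial with n = 60.

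| Scenario | Best arm, recomputed | Stated |
|---|---|---|
| A | 0.822 | .822 |
| B | 0.949 | .949 |
| C | 0.696 | .700 |
| D | 0.421 each | .421 each |

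The exact 90% interval at 54/60 is 0.812 to 0.956, width 0.143 (stated: 0.81 – 0.95, width 0.143). At 10 patients, P(rate ≤ 0.80) is 0.795 with 7 successes and 0.533 with 8, so the stated futility boundary of 7 or fewer is right. The small differences (0.696 against .700, 0.956 against 0.95) do not bear on this point.

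**Step 2: what Section 9.5 would show.** With x stable patients of 60, the posterior is beta(x + 0.5, 60 − x + 0.5). The limits are exact binomial.

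| x/60 | P(rate > 0.90) | P(rate > 0.80) | Exact 90% CI |
|---|---|---|---|
| 51 | 0.103 | 0.833 | 0.753–0.919 |
| 52 | 0.190 | 0.906 | 0.772–0.932 |
| 53 | 0.317 | 0.954 | 0.792–0.944 |
| 54 | 0.477 | 0.980 | 0.812–0.956 |
| 57 | 0.911 | 1.000 | 0.876–0.986 |

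The two posteriors do answer different questions. But the third column adds nothing to the fourth: at fixed n both are functions of the same count, and the planned interval already shows where 80% lies. Its lower limit passes 80% at 54/60.

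**Step 3: all four arms at 80%.** With 60 patients each and no interim stops, each arm leads strictly with probability 0.20937. A unique leader therefore appears in 4 × 0.20937 = 0.837 of trials, with a tie in 0.163. The median highest count is 51/60. The highest count is at most 53 with probability P(X ≤ 53)⁴ = (1 − 0.0308)⁴ = 0.882. So in 88.2% of such trials the interval of the top-ranked arm, tied tops included, contains 80%. At the median count the planned posterior is 0.10, which would not encourage anyone.

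**Step 4: futility.** Assume looks at 10, 20, 30, 40 and 50, with strict stopping at or below 7, 15, 22, 30 and 38 successes and no efficacy stop. An arm at 80% reaches 60 patients with probability 0.455, so 1 − 0.455 = 0.545 of null arms are removed. At least one of four null arms reaches 60 in 1 − (1 − 0.455)⁴ = 0.912 of trials.

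**Step 5: what a change would do.**

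- *An added P(rate > 0.80), without a bar.* It alters no selection. At 53/60 it reads 0.954 while the interval's lower limit is 0.792, so reading the two together settles nothing. It also ignores that the leader is the best of four: with all arms at 80%, the highest count reaches 52, hence a posterior of at least 0.90, in 41.9% of trials, and reaches 53, hence at least 0.95, in 24.2%.
- *A minimum count.* This would change conclusions, at a price. The Scenario A probability of selecting the 90% arm falls from 0.822 to 0.772, 0.701 or 0.583 with a bar of 52, 53 or 54.

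**The case for a change.** The strongest case is this. Section 9.3 asks whether any treatment halves deterioration, and ranking alone cannot answer that. The 90% posterior is near one half for an arm exactly on target, and a uniform prior gives much the same (0.41, against 0.97 for exceeding 80%). Futility does not close the gap, since 45.5% of null arms get through under strict use and Section 9.6 treats the posteriors as guidance. Stating the benchmark in advance costs two sentences and prevents a choice after the results are known.

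The arithmetic stands, and it is true that no passage prescribes a final reading against 80%. It does not follow that the plan is deficient. The 90% posterior speaks to the stated goal and matches the efficacy reference of Section 9.6. The interval supplies the comparison with 80%, and the 80% rate is printed in Section 9.3 before any result is known. A leader among equal arms belongs to every ranking design, and Section 9.1 discloses that this one tests nothing. An all-80% scenario would be informative, but the aim in Section 9.1 is conditional on a superior treatment existing, and the table serves that aim. What remains is a preference for an extra summary, and that summary can flatter a null leader more than the planned one does.

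**Conclusion.** The concern does not hold. Followed as written, the plan gives each arm's rate, an exact interval that shows whether 80% is excluded, and a posterior for the target; it applies 80% at the interim looks and defers definitive testing to later trials. No stated figure, rule or conclusion is wrong.

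The sizes that made it look serious are real but harmless here: 0.48 against 0.98 at 54/60 reflects two different questions, and the 83.7% unique-leader rate describes ranking as such. In 88.2% of all-null trials the planned interval itself would show that 80% has not been excluded. A minimum bar is a design trade-off for the sponsor, not the correction of an error.

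This rests on the beta(0.5, 0.5) prior carrying over to Section 9.5, on 60 patients per arm without interim stops for the leader figures, and on strict futility looks every 10 patients up to 50, without efficacy stops or replacement arms, for the continuation figures. The 80% is itself an assumed rate with no concurrent control, which limits how much any reading against it could prove.

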#### 4.9 Patient Registration to Treatment

To register a patient, the following information should be reviewed by the clinical research nurse (CRN) / clinical research associate (CRA) with the study physician per MCC SOPs to confirm eligibility:

- Copy of COVID19 testing results
- Mobile EKG tracing (outpatients) or standard EKG (inpatients) within 5 days of registration to assess QTc interval
- Eligibility labs, as well as correlative labs to be drawn
- Eligibility Checklist

Once eligibility is confirmed, the CRN/CRA will complete subject registration in the OnCore database (minimum data footprint) for randomization and complete study-required RedCap data forms. To complete the registration process, the CRN/CRA will:

- assign a patient study number
- register the patient on the study in OnCore
- receive the automated treatment arm assignment
- send an email or other communication to the study team of arm assignments.

If a patient is deemed ineligible for treatment their specimens will be retained in the COVID19 BIOBANK if the subject has indicated agreement to specimen collection and long-term storage in the consent form.

At the Day 1 visit or inpatient the following will be completed

- 1) Sign **treatment informed consent** (unless previously e-consented as above)
- 2) Undergo blood testing for eligibility (in subjects who have not had assessment of screening labs within the last 30 days will require blood draw)
- 3) Complete an eligibility questionnaire (age, concurrent diseases, current medications, contact information)
- 4) Undergo a mobile EKG or standard EKG tracing to assess QTc interval (within 5 days of registration)
- 5) Distribute medications, pill diary, and instructions
- 6) Baseline correlative blood sample
- 7) Sputum sample, with OP swab (alternative, if no sputum available)
- 8) Saliva sample
- 9) COVID-19 ordinal scale assessment (See Appendix B)
- 10) Limited visual physical exam unless a more complete exam is clinically indicated.

Day 3 or 4 phone call to assess clinical status and elicit concerns or questions.

Day 7 telehealth (+/- 4 days) is required for all patients to assess toxicity. If a subject has a standard of care telehealth visit during this period, this is also an acceptable toxicity assessment.

Day 10 or 11 phone call to assess clinical status and elicit concerns or questions

Day 14 (+/- 4 days) visit will also be completed in clinic or inpatient hospital.

- 1) Undergo blood testing for toxicity

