#### 4.10 General Guidelines

Following registration, patients should begin protocol treatment within 7 days. Issues that would cause treatment delays should be discussed with the Principal Investigator. If a patient does not receive protocol therapy following registration, the PI and the statistician must be consulted as soon as possible.

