#### 8.1.5 *Artemisia annua* tea and coffee

### Procurement

**Outpatients:** Coffee and tea botanical products will be directly shipped overnight to study patients, who are outpatients by Baesman on behalf of ArtemiLife. Patients without a pod coffee maker will also receive a coffee maker.

The distributor for *Artemisia annua* is as follows:

Baesman Distributors

[name]

[name]

Contact: [[contact]](mailto:[contact])

Subjects randomized to Arm E will have their information entered into the ordering portal of

*IMP: Artemisia annua, Artesunate, Camostat mesilate, Ivermectin,  
Study #: MCC-20-COVID-01-PMC  
Amendment 4 August 28, 2020*

Baesman Distributors website.

**Inpatients:** This botanical product will be dispensed by Artemilife to the IDS pharmacy.

Formulation

Decaf coffee: 450 mg per pod

Tea: 225 mg per bad

Preparation, Storage and Stability

Tea and coffee should be stored at room temperature.

Coffee: Dispense 42, 450 mg pods

Tea: Dispense 84, 225 mg bags

Administration

Refer to the treatment section for specific administration instructions

Patients should be instructed to brew 1 (450mg) coffee pod or 2 (225mg) tea bags in 8 oz of water three times per day Days 1-14.

Drug Interactions

Increased Effect/Toxicity: No known drug interactions

Decreased Effect: CYP2A6 strong inducers may reduce the effects of Artemisia annua

Herb/Nutraceutical Interactions: No known interactions

Pharmacokinetics

Absorption: well absorbed orally

Distribution: Not established

Metabolism: Metabolized by CYP2A6

Half-life elimination: 1hr

Terminal: Not reported

Excretion: Not known

Adverse Events

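### The primary m-ITT set drops randomised patients who are never dosed, so a deterioration before the first dose can leave the denominator instead of counting as a failure

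*Combined protocol and SAP*

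**What the plan says.** Section 9.5 defines the analysis set: "m-ITT population is defined as all patients who have been randomized and received at least one dose of the study treatment". It then names this set as the basis of the primary analysis. Missing endpoints are scored as non-response, but only for patients already in the m-ITT. No analysis of all randomised patients is planned, even as a sensitivity analysis.

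The timing comes from other sections:

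- **Assignment.** At registration, staff "receive the automated treatment arm assignment" (section 4.9).
- **Start of treatment.** "Following registration, patients should begin protocol treatment within 7 days" (section 4.10). For a patient who never receives therapy, the only instruction is to consult the PI and the statistician.
- **Endpoint clock.** Deterioration is assessed "within 14 days from study entry" (section 9.1), and section 9.5 counts response from enrolment and randomisation. Neither runs from the first dose.
- **Supply.** The Day 1 list in section 4.9 includes "Distribute medications, pill diary, and instructions". For Arm E, section 8.1.5 says "Coffee and tea botanical products will be directly shipped overnight to study patients, who are outpatients", and the order is placed once the arm is known: "Subjects randomized to Arm E will have their information entered into the ordering portal of" the distributor. Arm E inpatients are supplied through the pharmacy.

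**The concern.** The endpoint clock starts at study entry, but membership of the primary set depends on a later event, taking a first dose. Deterioration can prevent that event. A patient who worsens between randomisation and first dose, and for that reason never starts, meets the protocol's definition of failure and is still removed from numerator and denominator. Every such removal takes out a failure, so the bias is upward in any arm.

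This trial has little to absorb such a bias. It has no control arm and no between-arm test. The observed stability rates are read against 80% and 90%, drive the interim posterior probabilities, and rank the arms for selection. The 7-day allowance covers every arm, so inflation against the fixed benchmarks needs no difference between arms.

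**Working it through.** **The plan's own figures reproduce.** I took exact binomials with n = 60 in each of four arms and called an arm selected only if it strictly leads (ties select nobody). Scenario A of section 9.3 gives .822, as stated. Four arms all at .80 each have a sole-leader chance of .209. Under the Jeffreys prior of section 9.6, 7 stable of 10 gives P(rate ≤ .80) = .795, above the 70% limit, and 8 of 10 gives .533. So ≤ 7 of 10 is the correct bound, and the design arithmetic is not at fault.

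**Inputs.** From the documents: 14-day deterioration of 20% (section 9.3), a lag of up to 7 days (section 4.10), and overnight shipment for Arm E outpatients (section 8.1.5), taken as 1 day. Assumed, because the documents are silent: an inert drug, a constant hazard, and a fraction f of pre-dose deteriorators who are never dosed.

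**Formulas.**

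- Deteriorated by day t: F(t) = 1 − 0.8^(t/14)
- Patients lost per 60: 60 × f × F(t)
- Apparent stability: 0.80 / (1 − f × F(t))

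F(1) = 1 − 0.8^(1/14) = .0158, and F(7) = 1 − 0.8^(1/2) = .1056.

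| Lag | f | Lost per 60 | Apparent stability (true 80%) |
|---|---|---|---|
| 1 day | 0.5 | 0.5 | 0.80 / 0.9921 = 80.6% |
| 1 day | 1.0 | 0.9 | 0.80 / 0.9842 = 81.3% |
| 7 days | 0.1 | 0.6 | 0.80 / 0.9894 = 80.9% |
| 7 days | 0.5 | 3.2 | 0.80 / 0.9472 = 84.5% |
| 7 days | 1.0 | 6.3 | 0.80 / 0.8944 = 89.4% |

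**Interim look.** Section 9.6 triggers the first look at 10 randomised patients per arm but does not name the analysis set. Take 7 stable patients and 3 failures. Counted as 7 of 10, the posterior is .795 and the arm stops for futility. If one failure was never dosed and the m-ITT is applied, 7 of 9 gives P(rate ≤ .80) = .599 and the arm continues.

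**Selection between arms.** Put the 1-day wait in Arm E only, with all four arms truly at .80 and n kept at 60. Arm E's sole-leader chance moves from .21 to .24 (f = 0.5) or .27 (f = 1). If every arm waits and Arm E waits one day more, the result is nearly the same, .24 to .28 for common waits of up to 6 days. Where a rival arm is truly at .90, its selection probability falls from .822 to .813 (f = 0.5) or .801 (f = 1).

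**The case against.** Several points on the other side stand.

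- **Not every pre-dose deterioration disappears.** Only patients who are never dosed leave the set. Treatment may be given to inpatients (section 6.1), Arm E has an inpatient supply route, and hospital admission alone does not end treatment under section 6.3. Many who worsen could still be dosed and would count as failures, so f = 1 is an extreme and no document supports a particular value.
- **The documented arm difference is small.** A reader might infer that Arm E could look the winner by a wide margin. On the same model with f = 1, a 3-day wait in one arm alone gives a sole-leader chance of .43, and a 7-day wait gives .79. The documents do not support either case: the 7-day window covers all arms, and the only arm-specific wait is an overnight shipment to outpatients.
- **A worse starting baseline is speculative.** A reader might also infer that late starters are scored from an already lowered level. Section 4.9 scores the scale at the Day 1 visit, which for Arm E outpatients would come before the wait for delivery.
- **Refusal by arm has no documented size or direction.** The regimens are visibly different, so refusal before dosing could vary by arm, but nothing more can be said.
- **Selection is not the final test.** Section 9.1 says that later trials are needed, and section 9.6 lets clinical, safety and outside information guide decisions.

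The existing safeguards do not close the gap. Consultation under section 4.10 is not an analysis rule. The missing-data rule does not reach patients outside the m-ITT. Sections 6.1 and 6.3 count intensive care or intubation as primary failure without saying whether this covers a randomised, undosed patient, which leaves them unreconciled with section 9.5.

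**Conclusion.** The point holds. As written, section 9.5 can remove protocol-defined failures from the primary analysis, and the effect is upward in any arm. The size cannot be stated from the documents. Under an inert drug and 20% deterioration at constant hazard, the inflation of a true 80% runs from under 1 percentage point (1-day lag, half never dosed) to 9.4 points (7-day lag, none ever dosed). The upper figure is the limit of what section 4.10 permits, not a forecast.

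The main risk is inflation against the 80% and 90% benchmarks and the interim bounds. The effect on ranking from the documented Arm E shipment is modest, less than 1 patient in 60 on these assumptions.

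**What to change.** In section 9.5:

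1. Make all randomised eligible patients the primary set.
2. Fix the baseline scale at randomisation. Sections 9.1 (study entry), 12.1 (diagnosis) and 4.9 (Day 1 visit) now give different reference points.
3. Count deterioration after randomisation and before the first dose as failure, and never-dosed patients with no outcome as non-responders.
4. Keep the m-ITT as a sensitivity analysis.

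In section 9.6, state that the interim counts use the same primary set. Report by arm the number never dosed, the reasons, and the days from randomisation to first dose. Reconcile the Day 1 distribution in section 4.9 with the Arm E outpatient shipment in section 8.1.5; which route is used is for the sponsor to settle.

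The cost is a short text change and no added patients, since the 60 per arm in section 9.3 can be read as randomised. The downside is that a few undosed patients slightly dilute the rates, which the m-ITT sensitivity analysis will show.
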